4.2.3.4 Analysis of Exploratory Endpoints

4.2.3.4.1 SARS-CoV-2 RT-PCR-positive Symptomatic Illness

The incidence of SARS-CoV-2 RT-PCR-positive symptomatic illness will be summarized with descriptive statistics in the FAS at the final data readout only. The number and percentage of participants who have the events will be provided overall and before Day 183, or Day 365.

Participants will be included as an event if they have RT-PCR-confirmed SARS-CoV-2 prior to Day 183, or Day 365, after first IMP dose and present with at least one of the qualifying symptoms as defined in the CSP. A positive SARS-CoV-2 RT-PCR will be defined based on the central laboratory result whenever both central and local laboratory results are available for NP swabs, or if only a central lab NP swab result is available. If only a local NP swab laboratory result is available, then the local laboratory result will be used. If no SARS-CoV-2 RT-PCR results are available, the participant will be considered as not having a RT-PCR-positive symptomatic event. Data from the eCRF will be used to determine if the participant met the qualifying symptoms. If a participant's first case of SARS-CoV-2 RT-PCR positive symptomatic illness occurs on or after Day 183, or Day 365, the participant will be considered as not having an event, respectively. Death due to COVID-19 or hospitalization due to COVID-19 can contribute to this endpoint when a qualifying symptom assessment is not observed.

- For participants with an event after first IMP dose, before Day 183, or Day 365, the date of event will be defined as the earliest symptom onset date from those which triggered an illness visit, where COVID-19 was confirmed with a positive SARS-CoV-2 RT-PCR laboratory test. In the case of death due to COVID-19 or hospitalization due to COVID-19, the date of event is the earliest date of death/date of hospital admission when a qualifying symptom is not observed.

If any of the following censoring reasons are met, the censoring date will be defined as follows:

- Participants who had SARS-CoV-2 RT-PCR positive test prior to first IMP dose will be censored at date of first IMP dose.
- Participants who receive a COVID-19 vaccination after first IMP dose, and prior to having an event before Day 183, or Day 365 will be censored at the date of vaccination.
- Participants who have a protocol deviation for receiving restricted medication after first IMP dose, and prior to having an event before Day 183, or Day 365 will be censored at the date of the deviation.
- Participants who have a record-level exclusionary protocol deviation for PK samples (see Table 5 in most recent version of PDMP) after first IMP dose, and prior to having an event before Day 183, or Day 365 will be censored at the date of the deviation.
- Participants who discontinue early from the study after first IMP dose, and prior to having an event before Day 183, or Day 365 will be censored at date of end of study or date of last assessment, whichever is later. For participants who continue to participate in the study at the time of the analysis, the data cut off (DCO) date will be used as their last assessment date. For participants with no post-baseline visit data available, the date of the first IMP administration will be used i.e., follow-up will be 1 day.

The follow up time will be calculated as the minimum of the date of censoring, date of event, and date of Day 183 or Day 365 – date of first IMP dose + 1. When the minimum of the date of censoring and date of Day 183 or Day 365 is prior to date of event, then participants will be censored at their defined end of follow up time. Otherwise, participants will be identified as having an event at this time.

Time to the first SARS-CoV-2 RT-PCR-positive symptomatic illness episode will be analyzed using Kaplan-Meier (KM) method and quartiles will be presented. Proportion of participants who experience event, participants who are censored, breakdown of events, and reasons for censoring will be presented by treatment group at Day 183 or Day 365. KM plot will also be generated by treatment groups.

A listing will be provided for all COVID-19 symptom assessments and NP swabs assessed by RT-PCR (both local laboratory and central laboratory samples) regardless of RT-PCR result.

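### SAP 4.2.3.4.1 classifies an illness with onset exactly on Day 183 or Day 365 two ways, and does not say clearly whether the RT-PCR date or the onset date decides the cut-off

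*SAP*

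**What the plan says.** SAP 4.2.3.4.1 asks for two kinds of output in the full analysis set. One is a table of participants with symptomatic illness, overall and before Day 183 or Day 365. The other is a Kaplan-Meier analysis of time to the first episode, with the proportions having an event or being censored at the same cut-offs. Four of its rules bear on the cut-off:

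- **Inclusion.** "Participants will be included as an event if they have RT-PCR-confirmed SARS-CoV-2 prior to Day 183, or Day 365, after first IMP dose", together with at least one qualifying symptom.
- **Non-event.** If the first case "occurs on or after Day 183, or Day 365, the participant will be considered as not having an event".
- **Event date.** For confirmed cases, "the date of event will be defined as the earliest symptom onset date from those which triggered an illness visit". For COVID-19 death or hospitalisation, "the date of event is the earliest date of death/date of hospital admission when a qualifying symptom is not observed".
- **Event or censored.** "When the minimum of the date of censoring and date of Day 183 or Day 365 is prior to date of event", the participant is censored. In every other situation the participant is recorded as having an event.

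SAP 4.2.3.4.3 applies the same censoring criteria to severe or critical illness. Protocol 8.1.3 has the SARS-CoV-2 swabs taken at the first illness visit (IL-D1a), after symptoms have been reported and judged related to COVID-19, so the RT-PCR date will normally be the onset date or later.

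**The concern.** The non-event rule and the event-or-censored rule draw the line on different sides of the cut-off day. The first excludes a case falling on that day. The second censors only if the cut-off is strictly earlier than the event, so a tie counts as an event.

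The inclusion sentence raises a separate question. If its time limit attaches to the RT-PCR test, it uses a different date from the one that defines the event. A participant who falls ill shortly before Day 183 and is swabbed on or after it would then fail inclusion, while the follow-up rule would place an event before the cut-off.

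At stake is whether the incidence table and the Kaplan-Meier output, reported for the same cut-off, hold the same cases. As the text stands, the programmer has to settle both questions.

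**Working it through.** The plan gives no figure on this point to reproduce. The check codes each rule as a test and applies it around each cut-off C (183 or 365), with no other censoring.

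**Tests**

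- Inclusion, read as a cut on the test date: event if RT-PCR day < C.
- Non-event rule, using the onset-based event date: event if onset day < C.
- Follow-up rule: censored if C < onset day, otherwise an event; so event if onset day ≤ C.

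**Results**

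| Onset day | RT-PCR day | Inclusion (test-date reading) | Non-event rule | Follow-up rule | Follow-up (days) |
|---|---|---|---|---|---|
| 178 | 180 | event | event | event | 178 |
| 181 | 184 | no event | event | event | 181 |
| 183 | 183 | no event | no event | event | 183 |
| 184 | 185 | no event | no event | censored | 183 |
| 363 | 366 | no event | event | event | 363 |
| 365 | 365 | no event | no event | event | 365 |

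The rows for onset on Day 183 and Day 365 show the tie. It needs no assumption about lag and affects exactly one onset day per cut-off. The rows for onset on Day 181 and Day 363 show the date-basis problem, which arises only on the test-date reading.

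**How many onset days are affected.** With an onset-to-swab lag of L days, the inclusion test fails once onset + L ≥ C. Onset days C − L to C − 1 are then classified differently by the inclusion and follow-up rules. That is L days, plus day C itself for the tie: 1, 2, 4 or 8 days in all for L = 0, 1, 3 or 7.

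**Share of events.** The documents give neither the lag nor the spread of onset. Assume even onset over the C − 1 days before the cut-off and L = 1, 3 or 7:

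- Day 183: 1/182 = 0.5%, 3/182 = 1.6%, 7/182 = 3.8%. Tie: about 1/182 = 0.5%.
- Day 365: 1/364 = 0.3%, 3/364 = 0.8%, 7/364 = 1.9%. Tie: about 1/364 = 0.3%.

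**In participants.** No attack rate is given either. If 20 to 60 Day 183 events occurred among about 200 participants (assumed), the expected numbers are:

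- 3-day lag: 20 × 3/182 = 0.3 to 60 × 3/182 = 1.0.
- 7-day lag: 20 × 7/182 = 0.8 to 60 × 7/182 = 2.3.
- Tie: 20 × 1/182 = 0.1 to 60 × 1/182 = 0.3.

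With about 100 participants per arm, one reclassified case moves that arm's incidence by 1/100, or about 1 percentage point.

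**The case against.** The best defence is that the rules run in sequence: decide event status, assign a date, then compare that date with censoring. The event-date rule covers only participants who already have an event before the cut-off. Someone ruled out by the inclusion or non-event sentence would then have no event date and could not re-enter through the follow-up rule, so both outputs would agree. On this view the tie provision serves ordinary censoring dates, such as a vaccination on the day of onset.

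This reading is possible, and it is why a mismatch between the outputs cannot be called certain. It does not remove the conflict. If only cases before the cut-off carry an event date, the follow-up rule's comparison of Day 183 or Day 365 with that date has almost nothing left to do. The presence of that comparison suggests that event dates on or beyond the cut-off were expected, and for those the two inequalities disagree.

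A second defence concerns the inclusion sentence. It can mean an infection before Day 183 that is RT-PCR-confirmed, whenever the test was done. The section defines no RT-PCR date for cutting at Day 183 or 365; the only case dates it defines are onset, admission and death. This stands: the RT-PCR-versus-onset point is an ambiguity, not a proven contradiction. It leaves the tie untouched.

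A reader might also infer that late swabs are likely because Days 183 and 365 are site visits. The documents do not support that. Protocol Tables 1 and 2 schedule no RT-PCR swab at those visits, their windows are ±7 days, and Protocol 8.1.1 starts an illness visit as soon as possible once symptoms are judged related to COVID-19.

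**Conclusion.** The point holds in a limited form. The treatment of the cut-off day is inconsistent as written. The date that decides inclusion is ambiguous, and on one reading it would separate cases swabbed on or after the cut-off from their earlier onset.

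The effect is likely to be between no participants and a few at each cut-off. That rests on assumed lags of 1 to 7 days, even onset and an assumed number of events. Individual lags could be longer, since the monthly contacts ask about symptoms over the previous 30 days.

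A reader might go further and conclude that the two outputs will fail to reconcile, or that cases are lost. Neither follows. There may be no onset in the affected days, the table also reports incidence overall, and all symptom assessments and RT-PCR swabs are listed. The endpoint is exploratory, the summary is descriptive, no hypothesis is tested, and the same rules apply to both arms. Nothing here touches the primary endpoints. This is a minor correction.

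**What to change.** Make two wording changes in SAP 4.2.3.4.1:

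1. State that the event date decides whether a case falls before Day 183 or Day 365, in both the incidence table and the follow-up rule. The event date is symptom onset, or admission or death where no qualifying symptom is observed. Accept RT-PCR confirmation of that episode on any date.
2. In the follow-up rule, censor when Day 183 or Day 365 is on or before the event date. Change only this comparison, and leave ties with other censoring dates as they are.

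With both changes, onset on Day 182 or Day 364 is an event and onset on Day 183 or Day 365 is not, under every rule and whatever the swab date. The cost is two phrases in the SAP and the matching program line, with no new data. Because SAP 4.2.3.4.3 refers back to this section for censoring, check that the revised wording carries through there.

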9.3 Populations for Analyses

The following populations are defined in [Table 10](#).

Table 10 Populations for Analysis

Population/Analysis set	Description
Enrolled	All participants who sign the ICF.
Full analysis set	All randomized participants who receive at least one dose of IMP. Participants will be assigned according to their randomized treatment according to the intent-to-treat principle.
Safety analysis set	All participants who have received at least one dose of IMP. Participants will be assigned in this analysis set by the arm of treatment they actually received.
PK analysis set	All participants in the safety analysis set who received AZD7442 and who had at least one quantifiable serum PK observation post dose will be included in the PK analysis dataset.
ADA evaluable analysis set	All participants in the safety analysis set who have a non-missing baseline AZD7442 ADA result and at least one non-missing post-baseline AZD7442 ADA result.
nAb evaluable analysis set	All participants in the safety analysis set from whom blood samples are assumed not to be affected by factors such as protocol violations, and who had at least one quantifiable serum observation post dose. At any time during the study, participants will be excluded from this analysis set at the point at which they receive an alternative COVID-19 mAb.

ADA, antidrug antibody; COVID-19, coronavirus disease 2019; ICF, informed consent form; IMP, investigational medicinal product; nAb, neutralizing antibody; PK, pharmacokinetic.

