9.4.3 Exploratory Endpoints

9.4.3.1 SARS-CoV-2 RT-PCR-positive Symptomatic Illness

The incidence of SARS-CoV-2 RT-PCR-positive symptomatic illness will be summarized with descriptive statistics.

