4.2.3.4.2 Post-treatment Response for SARS-CoV-2 Nucleocapsid Antibodies

The incidence of participants who have a post-treatment response (negative at baseline to positive at any time post-baseline) for SARS-CoV-2 nucleocapsid antibodies will be summarized using FAS by treatment group overall and before Day 183, or Day 365 at the final data readout only. Same censoring criteria as described in Section 4.2.3.4.1 will be applied.

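### At Day 183 and Day 365 the SAP reclassifies some confirmed COVID-19 illnesses as censored but keeps those participants in the FAS denominator, so the reported incidence is understated

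*SAP*

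**What the plan says.** **Event definition.** SAP 4.2.3.4.1 reports the number and percentage of FAS participants with an event, overall and before Day 183 or Day 365. An event is an RT-PCR-confirmed infection after first dose with at least one qualifying symptom. COVID-19 hospitalization or death can stand in for the symptom. The definition does not mention vaccination or deviations.

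**Stops.** The same section then lists censoring reasons:
- Vaccination: the rule that begins "Participants who receive a COVID-19 vaccination after first IMP dose, and prior to having an event before Day 183, or Day 365 will be" ends follow-up on the vaccination date.
- A protocol deviation for restricted medication, censored on the deviation date.
- PK samples: the rule that begins "Participants who have a record-level exclusionary protocol deviation for PK samples (see Table 5 in most recent version of PDMP) after first IMP dose" works the same way, for deviations before an event, from the deviation date.

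**Consequence.** When the earlier of the censoring date and the cut-off falls "prior to date of event, then participants will be censored at their defined end of follow up time". Only otherwise is the participant an event.

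**Output.** "Proportion of participants who experience event, participants who are censored, breakdown of events, and reasons for censoring will be presented by treatment group" at each cut-off, with Kaplan-Meier quartiles and a plot. SAP 3.3 makes the analysis set the percentage denominator unless stated otherwise.

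**Reuse.** For nucleocapsid response (SAP 4.2.3.4.2): "Same censoring criteria as described in Section 4.2.3.4.1 will be applied". SAP 4.2.3.4.3 says the same for severe or critical illness and COVID-19 deaths. SAP 4.2.3.5 plans no sensitivity analysis for exploratory endpoints.

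**Protocol.** Section 9.4.3.1 says only: "The incidence of SARS-CoV-2 RT-PCR-positive symptomatic illness will be summarized with descriptive statistics". Table 7 and Section 6.5.1 allow COVID-19 vaccination except within 14 days before or after a dose.

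**The concern.** Censoring is a device for time-to-event estimation, where a censored participant also leaves the risk set. Here it feeds a simple proportion. A participant who is vaccinated and later has a confirmed illness meets the event definition, is tabulated as censored, and still counts in the FAS denominator.

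The resulting percentage has no clear meaning. It is not the incidence of all confirmed illness under the regimen, because observed cases are left out. Nor is it the incidence that would have been seen without vaccination, because participants who were stopped are treated as if followed event-free to the cut-off.

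Vaccination is mostly a permitted choice and the trial is open-label, so uptake may differ between arms. If it does, the understatement differs too. For deaths, SAP 4.3.2.1 separately summarizes COVID-19-related deaths without these stops, so one report could carry two death counts.

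**Working it through.** **The plan's own figure.** The documents give no figure for this endpoint. The only sample-size figure reproduces but does not bear on the point: 1 − 0.97^100 = 95.2%, against the stated 95%.

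**The rule applied to single participants (cut-off Day 365).**
- Vaccinated Day 150, ill Day 200: the minimum is Day 150, which precedes Day 200, so censored at Day 150.
- Vaccinated Day 150, ill Day 140: event at Day 140.
- No stop, ill Day 200: event at Day 200.

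The first and third participants have the same confirmed illness on the same day. Both are in the denominator, but only the third is in the numerator.

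**Size of the effect.** Illness rates, vaccination uptake and deviation rates are not in the documents, so these inputs are assumptions:
- I = true cumulative incidence at one year, constant hazard, λ = −ln(1 − I) per year.
- v = share of participants vaccinated at a time uniform over the year, independent of illness.

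An unvaccinated participant is counted as an event with probability I. A vaccinated one is counted only if ill before vaccination, which has average probability 1 − I/λ. So

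counted percentage = (1 − v)·I + v·(1 − I/λ).

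For I = 25%: λ = 0.2877 and 1 − I/λ = 0.1310.
- v = 20%: 0.8 × 0.25 + 0.2 × 0.1310 = 22.6%
- v = 40%: 0.6 × 0.25 + 0.4 × 0.1310 = 20.2%
- v = 60%: 0.4 × 0.25 + 0.6 × 0.1310 = 17.9%

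The shares of cases lost are about 10%, 19% and 29%, close to v/2. For I = 15% the counted percentages are 13.5%, 12.1% and 10.6%. Over I = 10% to 30% and v = 10% to 70%, about 5% to 34% of cases are lost.

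If uptake were 20% in one arm and 60% in the other, two arms with the same true 25% would read 22.6% and 17.9%, a gap of about 4.8 points. The unequal uptake is hypothetical.

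**Does Kaplan-Meier repair it?** Simulating the same scenario with 1,000,000 participants gives Kaplan-Meier incidence of 25.1% and 24.9% at 20% and 60% uptake, so the estimator recovers the truth when vaccination is unrelated to risk. But the SAP asks for quartiles and a plot, not for the estimate at Day 183 or Day 365. A first quartile exists only if estimated incidence reaches 25%. The only incidence figure planned at the two cut-offs is therefore the crude one. For severe illness, Kaplan-Meier estimates are optional.

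**The case against.** The case for the plan is substantial.

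- **Conflict with intent-to-treat.** A reader might infer that the SAP breaks a protocol definition of incidence over an intent-to-treat population. The text does not support this. Protocol 9.4.3.1 names no analysis set and no follow-up rule. The SAP makes the link to the FAS. In Protocol 9.3 the phrase is "Participants will be assigned according to their randomized treatment according to the intent-to-treat principle", which governs arm assignment in a set limited to dosed participants. The SAP is filling a gap, and its amendment history records that censoring rules were added. This objection stands.
- **Cases vanishing from the report.** A reader might also infer that confirmed illnesses and deaths disappear. They do not. COVID-19 is recorded as an AE (Protocol 8.3.5), AEs, SAEs and deaths are summarized without these stops (SAP 4.3.2), and all symptom assessments and RT-PCR results are listed. What is lost is event status in these exploratory tables. Numbers censored and reasons are shown by arm, so the effect is partly visible.
- **The PK-sample stop.** It is tempting to say that an unusable sample has no bearing on illness. Table 5 of the protocol deviation management plan is not in the documents, so the triggers are unknown. SAP 4.2.2.4.1 excludes all PK samples after such a deviation and treats mistimed samples separately. That would fit deviations affecting later exposure, for which a stop could be coherent. What stands is that the SAP gives no reason.
- **Choice of estimand.** Stopping at vaccination is defensible when the question is the effect of AZD7442 alone, and it parallels the nAb exclusions in SAP 4.2.2.4.2. That justifies a supportive analysis, but not dividing its events by the whole FAS.
- **The overall count.** The vaccination and deviation stops are worded for Day 183 and Day 365. The overall count may already be uncensored, but the SAP does not say so.

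**Conclusion.** The point holds as an inconsistency within SAP 4.2.3.4.1, carried into 4.2.3.4.2 and 4.2.3.4.3. The event definition has no vaccination or deviation condition, the follow-up rule removes event status after a stop, and the crude FAS percentage keeps the stopped participants in the denominator. The rules are also missing from SAP Section 2, which lists only the nAb change.

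The understatement at Day 183 and Day 365 is certain in direction once any confirmed illness follows a stop. Its size cannot be known from the documents. The loss of about half the uptake share rests on constant hazard, uniform vaccination times and independence of vaccination from illness risk. No difference between arms is shown, only that one could arise. The endpoints are exploratory and no hypothesis is tested, so sample size and error rates are unaffected.

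**What to change.** In SAP 4.2.3.4.1 to 4.2.3.4.3:

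1. Add the number and percentage of FAS participants with a confirmed event after first dose, regardless of vaccination or deviation, overall and before Day 183 and Day 365. State that the overall count is uncensored.
2. Keep the censored analysis, labelled as supportive. Report its incidence as the Kaplan-Meier estimate at Day 183 and Day 365, not as a crude FAS percentage.
3. Justify the PK-sample-deviation stop for clinical events by naming the triggers in the deviation management plan, or drop it.
4. List the censoring rules in SAP Section 2.

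The cost is SAP wording and a few table rows, since the data are already collected. The downside is that the uncensored figure includes illness after vaccine plus AZD7442, which a footnote should say.

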7.3 Lost to Follow-up

A participant will be considered lost to follow-up if he or she repeatedly fails to return for scheduled visits and is unable to be contacted by the study site.

The following actions must be taken if a participant fails to return to the clinic for a required study visit:

- The site must attempt to contact the participant and reschedule the missed visit as soon as possible and counsel the participant on the importance of maintaining the assigned visit schedule and ascertain whether or not the participant wishes to and/or should continue in the study.
- Before a participant is deemed lost to follow-up, the Investigator or designee must make every effort to regain contact with the participant (where possible, a minimum of 3 telephone calls and, if necessary, a certified letter to the participant's last known mailing address or local equivalent methods). These contact attempts should be documented in the participant's medical record. If after every effort to regain contact with the participant, they do not come in for their next visit, the participant may be considered lost to follow-up.
- Site personnel, or an independent third party, will attempt to collect the vital status of the participant within legal and ethical boundaries for all participants randomized, including those who did not get investigational product. Public sources may be searched for vital

status information. If vital status is determined as deceased, this will be documented, and the participant will not be considered lost to follow-up. Sponsor personnel will not be involved in any attempts to collect vital status information.

Discontinuation of specific sites or of the study as a whole are handled as part of [Appendix A](#).

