8.3 Adverse Events and Serious Adverse Events

The Investigator is responsible for ensuring that all staff involved in the study are familiar with the content of this section

The definitions of an AE or SAE can be found in [Appendix B](#).

Adverse events will be reported by the participant (or, when appropriate, by a caregiver, surrogate, or the participant's legally authorized representative).

The Investigator and any designees are responsible for detecting, documenting, and recording events that meet the definition of an AE.

8.3.1 Time Period and Frequency for Collecting Adverse Event and Serious Adverse Event Information

Non-serious AEs will be collected from the time of IMP administration through the last contact with the participant.

Serious adverse events will be recorded from the time of signing of the ICF through the last contact with the participant.

If the Investigator becomes aware of an SAE with a suspected causal relationship to the IMP that occurs after the end of the clinical study in a participant treated by him or her, the Investigator shall, without undue delay, report the SAE to the Sponsor.

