Summary of AEs and SAEs post the first dose of IMP will be broken down further by maximum severity. Severity, adapted from the CTCAE v5.0 (see Appendix A 2), will be classified as Grade 1 (mild), Grade 2 (moderate), Grade 3 (severe), Grade 4 (life-threatening or disabling), and Grade 5 (death) by using grading for AEs. Severity for AEs will be collected on “Adverse Events” form of eCRF. Should a participant experience multiple events within a SOC or PT, only the participant’s worst severity grade will be counted for that SOC or PT.

Relationship to IMP/Study Procedure

Relationship to IMP/ study procedure, as indicated by the Investigator, will be classified as not related or related. Should a participant experience multiple events within a SOC or PT, the participant will be counted as related for that SOC or PT if the event is related to either IMP or study procedure.

Exposure adjusted rate

Exposure adjusted rate is calculated as number of participants with AEs in categories divided by total participant-year follow-up for each treatment group. Participant years is determined by summing the total number of follow-up days of each participant, and then dividing by 365.25. The exposure period is calculated from time of first dose to end of study, or the current data cut-off, whichever is earlier.

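### Censoring early discontinuers at the later of end-of-study date and last assessment can count unobserved days after loss to follow-up as COVID-free time; the effect is small, and nil if sites enter the last-contact date.

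*SAP*

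**What the plan says.** SAP 4.2.3.4.1 sets the follow-up rules for RT-PCR-positive symptomatic illness.

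- Participants who discontinue the study early "will be censored at date of end of study or date of last assessment, whichever is later".
- Anyone still under follow-up at the analysis is treated as last assessed on the cut-off day.
- One exception shortens follow-up: "For participants with no post-baseline visit data available, the date of the first IMP administration will be used i.e., follow-up will be 1 day".
- Follow-up runs from first dose to the earliest of censoring, event, and Day 183 or Day 365. If censoring comes before the event date, the participant counts as censored.
- "Time to the first SARS-CoV-2 RT-PCR-positive symptomatic illness episode will be analyzed using Kaplan-Meier (KM) method and quartiles will be presented".

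SAP 4.2.3.4.2 (nucleocapsid response) and 4.2.3.4.3 (severe or critical illness) reuse the same censoring criteria.

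Protocol 7.3 requires attempts to regain contact, and only if, after these, "they do not come in for their next visit, the participant may be considered lost to follow-up".

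On adverse events, Protocol 8.3.1 says "Non-serious AEs will be collected from the time of IMP administration through the last contact with the participant". The denominator of the exposure-adjusted rate is set in SAP 4.3.2.1: "The exposure period is calculated from time of first dose to end of study, or the current data cut-off, whichever is earlier".

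Neither document defines a participant-level end-of-study date. Protocol 4.4 defines the end of the study only for the study as a whole.

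**The concern.** A censoring date should mark the last time at which an event would have been seen. When the end-of-study date falls after the last contact, the later-of rule picks the date with no observation behind it. The days between stay in the denominator of the Kaplan-Meier hazard but can contribute almost no events, so estimated incidence is pulled down.

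The same bullet follows the opposite principle elsewhere: a participant with no post-baseline visit data gets 1 day of follow-up. Someone seen once on Day 29 and then lost can be carried to whatever end-of-study date is entered.

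The adverse event denominator can likewise outlast the period in which events are collected. No Day 183 or Day 365 cap applies there, and exposure-adjusted incidence is a primary endpoint.

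**Working it through.** **The plan's own figure.** The only design figure is the 95% chance of at least one AE in 100 participants at a true rate of 3%: 1 − 0.97^100 = 0.952. It reproduces. The point here does not depend on it.

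**One participant.** Take an Arm B participant seen on Day 92, with a last monthly contact about Day 122 (assumed: 92 + 30), who misses Day 183. The next scheduled Arm B contacts (Protocol 1.3, Table 2) are Day 190 (remote or in person), Day 212 and Day 274. The site closes the participant at one of these.

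| Analysis | Follow-up ends under the SAP rule | Last contact | Unobserved days |
|---|---|---|---|
| Day 183 (cap applies) | 183 | 122 | 183 − 122 = 61 |
| Day 365, closed Day 190 | 190 | 122 | 190 − 122 = 68 |
| Day 365, closed Day 212 | 212 | 122 | 212 − 122 = 90 |
| Day 365, closed Day 274 | 274 | 122 | 274 − 122 = 152 |

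In the Day 183 analysis this is one third of that participant's follow-up (61/183 = 0.33). If the monthly contact is not credited, the gap from Day 92 to Day 183 is 91 days. For the adverse event denominator, 68 to 152 days is 68/365.25 = 0.19 to 152/365.25 = 0.42 participant-years for this one person.

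**The Kaplan-Meier estimate.** The documents give no incidence, loss rate or gap, so all three are assumed.

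- Event hazard λ = −ln(1 − incidence)/365; loss hazard d = −ln(1 − loss)/365; both constant.
- Observed and at risk: A(t) = exp(−(λ + d)t).
- Lost in the last g days but still counted at risk: G(t) = [d/(λ + d)] × [exp(−(λ + d)(t − g)) − exp(−(λ + d)t)], with t − g set to 0 when negative.
- The Kaplan-Meier hazard becomes λA/(A + G); incidence is 1 − exp(−its integral to Day 365).

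Worked case: incidence 20%, loss 10%, gap 91 days.

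- λ = 0.22314/365 and d = 0.10536/365, so λ + d = 0.000900 per day.
- After Day 91, G/A = (0.10536/0.32850) × (e^0.0819 − 1) = 0.3207 × 0.0854 = 0.0274, which lowers the hazard by 0.0274/1.0274 = 2.7%.
- Before Day 91 the reduction grows from 0 and averages about 1.3%.
- Weighted reduction: 2.66% × 274/365 + 1.34% × 91/365 = 2.3%.
- Cumulative hazard 0.22314 × 0.977 = 0.218, so incidence is 1 − e^−0.218 = 19.6% instead of 20.0%.

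Day 365 incidence (%) across the assumed range:

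| True incidence | Loss | Gap 30 d | Gap 91 d | Gap 182 d |
|---|---|---|---|---|
| 10 | 5% | 9.96 | 9.89 | 9.82 |
| 10 | 20% | 9.83 | 9.54 | 9.23 |
| 20 | 10% | 19.85 | 19.58 | 19.28 |
| 20 | 20% | 19.69 | 19.13 | 18.50 |
| 30 | 5% | 29.90 | 29.71 | 29.49 |
| 30 | 20% | 29.56 | 28.76 | 27.83 |

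The fall runs from 10.00 − 9.96 = 0.04 to 30.00 − 27.83 = 2.17 percentage points.

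**The case against.** The strongest objection is that the bias needs an end-of-study date entered after the last contact, and the documents do not say how that date is entered. If sites record the last contact, nothing changes. This stands, and it is why the effect is conditional. But the SAP does not require that convention, and the rule prefers the later date whenever the two differ.

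A reader might infer that everyone who leaves early is affected. The documents do not support that. Withdrawals have an Early Discontinuation Visit where possible (Protocol 7.2), and participants affected by the sponsor's termination have one too (Protocol 7.4), so the two dates should then coincide. The problem lies mainly with loss to follow-up.

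A reader might also infer that nothing can be recorded in the gap. Protocol 7.3 seeks vital status, including from public sources, and SAP 4.2.3.4.1 counts a COVID-19 death or hospitalization without a symptom assessment. A later successful contact also asks about symptoms since the previous one (Protocol 8.1.1). So some events can still surface, and a fix that simply censors at last contact would drop a COVID-19 death found afterwards.

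The rule that a missing RT-PCR result means no event classifies events under any censoring date. It does not add to this bias.

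Finally, the illness endpoint is exploratory, no hypothesis is tested, and reasons for censoring are tabulated by arm. At 20% incidence and 100 per arm, the binomial standard error is √(0.2 × 0.8/100) = 4 points, well above the 0.4-point shift in the worked case. This limits the consequence; it does not justify the rule.

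**Conclusion.** The point holds for participants lost to follow-up and for withdrawals without an Early Discontinuation Visit. Where their end-of-study date is later than their last contact, the SAP rule adds unobserved time as event-free time and lowers estimated COVID-19 incidence. In the Arm B example this is 61 days in the Day 183 analysis and 68 to 152 days in the Day 365 analysis. For Day 365 Kaplan-Meier incidence the fall is about 0.04 to 2.2 points under assumed incidence of 10-30%, loss of 5-20% and gaps of 30-182 days. It is nil if sites enter the last-contact date.

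Three stronger readings go beyond the documents.

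- **Carried to the cap.** If the study-level definition in Protocol 4.4 were applied to individuals, everyone lost would be carried to Day 365, and the fall could reach 30.0 − 27.1 = 2.9 points. The SAP does not say that this is meant.
- **A biased arm comparison.** Visit spacing differs (Arm A has a Day 121 visit), but no loss figures by arm are given, so a difference in bias is only possible.
- **A material error in the primary safety rates.** The denominator in SAP 4.3.2.1 has the same weakness, but it rests on the same undefined date, and the documents give no loss figures from which to size the effect.

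**What to change.** In SAP 4.2.3.4.1, replace the rule for early discontinuation along these lines:

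- A participant who discontinues early without a recorded event is censored at the last date on which COVID-19 status was ascertained: the last visit, illness visit, or recorded monthly contact with a response. If contact dates are not in the database, use the last recorded visit or assessment. The date is not later than the participant's end-of-study date.
- A COVID-19 death or hospitalization documented from another source, such as the vital-status search, stays an event at its own date even if that is after the last contact. Show such events separately in the planned breakdown, because non-events are not followed over the same period.
- Define the participant-level end-of-study date. Leave the other censoring reasons and the 1-day rule as they are.

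SAP 4.2.3.4.2 and 4.2.3.4.3 inherit the change by cross-reference. In SAP 4.3.2.1, end participant-years at last contact for participants lost to follow-up or withdrawn, to match the collection period in Protocol 8.3.1.

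The cost is SAP wording, one derived date and slightly less person-time. The documents describe the monthly contacts but do not say that dated responses are entered in the database; hence the fallback to the last recorded visit or assessment.
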